# 17.4.8.2. Analysis

Descriptive statistics will be presented split by treatment and overall for duration of PICU stay and hospital stay separately (before they have been transformed). The summaries will be presented as median and interquartile range as the data is likely to be skewed.

The comparative analysis will be as described in 17.4.1.2 for the duration of PICU stay and hospital stay, but will just involve the two-sample t-test, a linear mixed effects model will not be used for this outcome.

**17.4.9.** Secondary Outcome 8: Liverpool Respiratory Symptom Questionnaire The "Liverpool Respiratory Symptom Questionnaire" (LRSQ) score, a parent reported outcome measure of respiratory symptoms, at 6m (+/-1m) and 12m (+/-1m) [6]. The parents of infants randomised in season 3 will only complete the 6m questionnaire.

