5 TRIAL SETTING AND SELECTION OF SITES & CLINICIANS

Approximately fourteen Paediatric Intensive Care Units (PICUs) in the United Kingdom that routinely mechanically ventilate critically ill infants with high caseloads of bronchiolitis will recruit to BESS. Pls for sites that have provisionally agreed to participate in BESS have shared local activity data, commented on the application and are recognised as co-applicants on the application award. The Pls will champion the study at the sites and take local responsibility for the conduct of the trial. Pls will identify local co-Investigators.

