11.3 Sample Size calculation

The study will be powered to detect a minimally clinically important difference of 18 hours (0.75 days) in the primary outcome variable of time of mechanical ventilation. Data are expected to be positively skewed, and will therefore be log-transformed, and resulting data back-transformed. The null hypothesis is that of no difference in time of MV between the two groups.

Data from Alder Hey Children's Hospital from an audit of 60 eligible infants admitted to PICU in the seasons 2012/3 and 2013/4 showed a mean (SD) duration of ventilation of 4.83 (2.5) days (PICANet data, 2011-14). Parameters for sample size estimation are therefore as follows:

```
E(Y_1) = 4.83 \text{ and } SD(Y_1) = 2.5 E(Y_2) = 4.08 \text{ and } SD(Y_2) = 2.5 \delta = E(Y_2)/E(Y_1) = 0.845 giving coefficients of variation: \kappa_1 = SD(Y_1)/E(Y_1) = 2.5/4.83 = 0.518 \kappa_2 = SD(Y_2)/E(Y_2) = 2.5/4.08 = 0.613
```

Using the formula of Wolfe and Carlin (1999) with r = 1 for equal allocation and a two-sided alphalevel of 0.05, sample size estimations are 100 per group for 80% power and 134 per group for 90% power.

Taking the sample size of 134 and allowing for 5% dropout requires 142 patients will be recruited to each group, giving a total of 284 participants overall.

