#### 8.7. Method of assignment to treatment

Participants will be randomised to receive either poractant alfa or air placebo in a 1:1 ratio. The randomisation list will be generated by an independent statistician at the LCTC who is not otherwise involved in the BESS trial. Randomisation lists will be computer-generated using block randomisation, stratified by site and duration of ventilation (<24hrs and >=24hrs) prior to randomisation.

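### The five secondary duration outcomes are compared by an unadjusted t-test despite stratified randomisation, so their intervals are somewhat too wide to the extent that site and prior ventilation predict duration

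*SAP*

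**What the plan says.** - **Design.** SAP 8.7 (and Protocol 11.2) describes 1:1 blocked randomisation, "stratified by site and duration of ventilation (<24hrs and >=24hrs) prior to randomisation". Protocol 5 plans for "Approximately fourteen Paediatric Intensive Care Units (PICUs) in the United Kingdom", so there are about 14 × 2 = 28 strata.
- **Secondary durations.** SAP 17.4.2.2 (SBT readiness), 17.4.5.2 (oxygen), 17.4.7.2 (post-extubation support) and 17.4.8.2 (PICU and hospital stay) each refer back to the log-scale comparison of 17.4.1.2 "but will just involve the two-sample t-test, a linear mixed effects model will not be used for this outcome". No reason is given.
- **Where the SAP does adjust.** For the primary outcome, 17.4.1.2 adds to the t-test a mixed model with prior ventilation, sex and adjusted age as fixed effects and site as a random intercept. The SF ratio model (17.4.4.2) and the LRSQ model (17.4.9.2) include prior ventilation and a random intercept for centre or site.
- **Protocol requirement.** Protocol 11.5 asks for the stratification factors in the primary analysis. It says nothing equivalent about secondary durations.
- **Intervals.** SAP 12 promises 95% intervals for all point estimates and plans no multiplicity adjustment.

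**The concern.** Stratified blocking makes the arms nearly equal within each site and prior-ventilation group. Differences between strata therefore contribute almost nothing to the difference between arms. A two-sample t-test takes its standard error from the total variance, which still contains those differences. If the strata are prognostic, the reported standard error exceeds the true one. A nominal 95% interval then covers more than 95% of the time, and the test rejects less often than 5% under the null.

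At stake is the precision of five efficacy outcomes that give context to the primary result. The SAP is also uneven: it treats these factors as worth adjusting for in three other analyses and excludes them here without explanation.

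**Working it through.** **1. The plan's own figure.** Protocol 11.3 gives control data that "showed a mean (SD) duration of ventilation of 4.83 (2.5) days", a treated mean of 4.08 with SD 2.5, and the cited formula for a log-transformed outcome "with r = 1 for equal allocation and a two-sided alphalevel of 0.05".

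- Log variances, ln(1 + CV²): ln(1 + 0.518²) = 0.2374 and ln(1 + 0.613²) = 0.3188; sum 0.5562.
- Log geometric-mean difference: ln(4.08/4.83) − 0.5 × (0.3188 − 0.2374) = −0.2095.
- n per arm = (z for α/2 + z for power)² × 0.5562 / 0.2095² = 99.5 at 80% and 133.2 at 90%.
- Dropout: 134/0.95 = 141.05, so 142 per arm and 284 in total.

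This reproduces "sample size estimations are 100 per group for 80% power and 134 per group for 90% power" and the recruitment target. It concerns the primary outcome only; no power is stated for any secondary duration. It is used below only to set the simulation's arm size and log SD (0.527).

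**2. Formulas.** Let R² be the share of log-duration variance explained by the strata, and s = √(1 − R²). With arms balanced within strata, the true standard error is s times the one the t-test uses. Sample size cancels.

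- Excess interval width = 1/s − 1
- True two-sided size = 2Φ(−1.960/s); coverage = 1 − size
- t-test power for an effect with 80% power under the adjusted model = Φ(2.802 − 1.960/s), where 2.802 = 1.960 + 0.842

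At R² = 10%: s = √0.90 = 0.9487; 1/s − 1 = 5.4%; 1.960/s = 2.066; size = 2Φ(−2.066) = 0.039; power = Φ(0.736) = 76.9%.

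| R² (assumed) | s | Excess width | True size | True coverage | t-test power |
|---|---|---|---|---|---|
| 0% | 1.000 | 0 | 0.050 | 95.0% | 80% |
| 5% | 0.975 | 2.6% | 0.044 | 95.6% | 78.5% |
| 10% | 0.949 | 5.4% | 0.039 | 96.1% | 76.9% |
| 20% | 0.894 | 11.8% | 0.028 | 97.2% | 72.9% |

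**3. The same loss from the other side.** Suppose instead that the effect has 50% power when the strata are ignored. The t-test keeps 50%, while the adjusted analysis reaches 52.0, 54.2 or 59.1% at R² of 5, 10 or 20%. For 90% nominal power, the pairs (t-test against adjusted) are 90.6/91.4, 91.2/92.7 and 92.4/95.2%.

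**4. Simulation check.** 268 infants, 14 sites × 2 strata, blocks of 2 or 4 (assumed), 3,000 runs, adjusted model with site as fixed effects.

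- t-test width relative to adjusted width: 1.02, 1.05 and 1.11 at R² of 5, 10 and 20%. At R² = 0 it was 0.998, so needless adjustment cost about 0.2%.
- Rejection under the null, t-test against adjusted: 0.055/0.057, 0.042/0.053 and 0.027/0.049.

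The Monte Carlo standard error is about √(0.05 × 0.95/3000) = 0.004. The runs show clear conservatism at 20%, but at 5% they show no departure from nominal size.

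**5. Which outcomes can be logged.** SAP 17.4.5.1 and 17.4.7.1 assign zero when no oxygen supplementation or no NIV is recorded. SAP 17.4.8.1 assigns zero hospital time after death in PICU. ln(0) does not exist, so neither the t-test nor a mixed model on logs can include those infants as written. SBT readiness and PICU stay have no assigned zeros.

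**The case against.** The case for leaving the plan alone has real force. The exclusion is explicit in four subsections, so it is a choice and not an oversight. Protocol 11.5 asks for the stratification factors only in the primary analysis, so nothing is breached. The error is conservative, and with many secondary outcomes and no multiplicity adjustment, mild conservatism threatens no conclusion. All of that stands. It lowers the importance of the point, but it does not give a reason to report a standard error known to be too large when the SAP already specifies the model that corrects it.

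Three stronger inferences are tempting, and the documents do not support them.

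- *That real effects will be missed.* The size of the loss depends on R², which is not reported. It is nil at R² = 0 and at most about 4 power points up to 10%. The t-test does not lose power against its own nominal value when that value is 50% or more; the loss is only relative to the adjusted analysis.
- *That the t-test is equivalent to discarding 5, 10 or 20% of the infants.* This is true of interval width but not of power. At R² = 20% the t-test has 72.9% power, whereas discarding 20% of infants gives Φ(2.802 × 0.894 − 1.960) = 70.7%.
- *That the stay outcomes suffer most because discharge follows local practice.* Neither document says so. The one relevant statement, in Protocol 4.2, is that weaning and extubation are standardised across sites, which would limit site variation in SBT readiness.

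**Conclusion.** The point holds as a matter of efficiency and consistency. All five secondary durations are analysed without the factors used to stratify randomisation, although the SAP uses those factors in the primary mixed model, SF ratio and LRSQ analyses. To the extent that the strata are prognostic, the intervals over-cover and the tests are conservative. The estimates are not biased, and false positives are not increased.

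For an assumed R² of 5 to 20%, intervals are about 2.6 to 11.8% too wide, true size is about 0.044 to 0.028, and 80% adjusted power becomes about 78.5 to 73%. These figures assume roughly normal log durations, a constant treatment effect and near-balance within strata. They cannot be relied on for oxygen, post-extubation support or hospital stay until the zeros are dealt with.

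**What to change.** In SAP 17.4.2.2, 17.4.5.2, 17.4.7.2 and 17.4.8.2, delete the exclusion of the mixed model and specify:

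> The between-arm ratio and its 95% confidence interval will come from a linear mixed model on log duration, with prior-ventilation stratum (<24h, ≥24h) as a fixed effect and site as a random intercept. The unadjusted two-sample t-test will be reported as a supplementary line.

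Sex and adjusted age may be added to match 17.4.1.2. They are not stratification factors, so this point does not require them.

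This can be applied at once to SBT readiness and PICU stay. For oxygen, post-extubation support and hospital stay, first state how the zeros assigned in 17.4.5.1, 17.4.7.1 and 17.4.8.1 are handled. The t-test needs that rule just as much as the mixed model does.

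The cost is wording in four subsections, a rule for the zeros, and modest programming. Site and stratum are needed to randomise, so they should be available for every infant, and sex and age are listed baseline variables (SAP 17.2). No new data are needed. The change should be dated in the SAP's change control before randomisation codes are released to the statistical team.

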# 17.4.9.1. Derivation

The LRSQ will be captured in the Form 2 6 Months LRSQ and Form 3 12 Months LRSQ in JotForm. The LRSQ consists of eight domains, each containing between three and five items. The first six domains assess respiratory symptoms and the remaining two assess the impact of symptoms on the child and family. Parents will be asked to consider symptoms over the last 3 months, with questions being scored on a five-point Likert scale from "not at all" (score 0) to "every day" (score 4). A score for each domain and for the complete questionnaire will be calculated (maximum score 128) [6].

The domains and the symptoms they assess are listed in the table below:

Que	stionnaire domain	Symptoms assessed
1.	Daytime symptoms	Cough, wheeze, shortness of breath, "rattly"
2.	Symptoms with colds	chest
3.	Interval symptoms (between colds)	
4.	Symptoms with activity	
5.	Night-time symptoms	Cough, wheeze, shortness of breath, "rattly"
		chest, snoring
6.	Other symptoms	Noisy breathing not from chest, noisy breathing
		from throat, fast breathing
7.	Effects on child	Feeding, activity levels, sleep disturbance,
		fatigue

8.	Effects on family	Family activities, adjustment to family life,
		disturbed sleep, worry/anxiety

# 17.4.9.2. Analysis

Descriptive statistics will be presented split by treatment and overall for LRSQ scores for 6 months, 12 months and the difference (12-month – 6-month) where available. The summaries presented will be the number, number missing, mean and standard deviation.

A linear mixed effects model will be fitted using ANCOVA to test for a difference between groups 12month LRSQ score with adjustment for 6-month LRSQ score and the stratification factors of time on ventilation prior to randomisation (<24h and  $\geq$ 24h) as a fixed effects and site as a random effect (random intercept only). The between-group difference and corresponding 95% confidence interval will be reported.

This will be a complete case analysis and only fully completed questionnaires will be included in the analysis.

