3.5.3 Secondary Objective(s)

- 1. To describe the impact of intervention on infants' long-term respiratory symptoms
- To describe secondary outcomes of efficacy including physiological indices and duration of other modes of respiratory support.
- 3. To assess the safety of the intervention for infants with life-threatening bronchiolitis

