Primary Objective To determine the efficacy of endotracheal surfactant in reducing total duration of MV by 18 hours or more, by random blind allocation of infants to receive either up to 3 doses of poractant alfa or up to 3 doses of air-placebo in an identical administration procedure.	Total duration of MV (hours) from randomisation to final extubation, including any time off MV due to failed extubation.	N/A
Secondary Objective 1 To describe the impact of intervention on infants' long term respiratory symptoms	The score (value) of patient reported outcome measure of respiratory systems in the "Liverpool Respiratory Symptom Questionnaire" (LRSQ)	LRSQ at 6 months and 12 months post randomisation
Secondary Objective 2 To describe secondary outcomes of efficacy including physiological	Time from randomisation to meeting study criteria for readiness for Spontaneous Breathing Test	N/A
indices and duration of other modes of respiratory support	Number of trial interventions given Change over time from baseline of Ventilation Index (VI), Oxygenation Index (OI) and Oxygenation Saturation Index (OSI) while mechanically ventilated, & SpO ₂ /FiO ₂ (SF) ratio Duration of oxygen supplementation Use of steroids to assist extubation	N/A Capillary blood gas sampling immediately prior to intervention and then at 6, 12, 24, 36 and 48hrs while still on MV; to continue daily after 48hrs if still on MV. N/A N/A

IRAS 220853 Page **22** of **87**

	Duration of post-extubation non-invasive respiratory support Duration of stay on PICU and in hospital	N/A N/A
Secondary Objective 3 To assess the safety of the intervention for infants with life-threatening bronchiolitis	Failure to administer the intervention due to any adverse event during preparatory processes (tracheal toilet or BAL)	Randomisation to 24 hours after final trial intervention
	Failure to complete administration of the intervention due to any adverse event during administration of the intervention (regardless of which arm of allocation)	Randomisation to 24 hours after final trial intervention
	Incidents of 'air leak' (pneumothorax and pneumomediastinum) occurring before discharge from PICU	Randomisation to discharge from PICU
	Other adverse events and serious adverse events associated with the intervention	Randomisation to 24 hours after final trial intervention
	Any need to replace the endotracheal tube	Randomisation to successful extubation

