8.6 Other Assessments

8.6.1 Parent Reported Quality of Life questionnaires

The parent reported outcome measure the Liverpool Respiratory Symptom Questionnaire (LRSQ), is a web-accessible questionnaire that has been optimised for many platforms

IRAS 220853 Page **40** of **87**

including smart-phones. Links to the form will be emailed to parents prior to the intended completion dates (in all three seasons at 6m, and in addition at 12m to parents of infants recruited in seasons 1 and 2). A paper version is available with a "free-post" return envelope.

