11.5 Analysis Plan

A full SAP will be written prior to the conduct of any comparative analysis of the treatment arms. The main features of the SAP are included here.

The primary analysis will be a test of the difference in geometric mean durations of MV between groups (placebo vs. poractant alfa), reported with the corresponding 95% confidence interval. The analysis will be conducted according to the intent-to-treat principle, and will incorporate the stratification factors of duration of ventilation (<24hrs and >=24hrs) prior to randomisation and site.

For the secondary outcomes, longitudinal data for VI, OI, OSI and SF will be analysed with joint modelling. LRSQ data will be modelled longitudinally and comparisons made between groups. Binary data will be reported in terms of relative risk with 95% confidence intervals.

Within BESS, data will be collected as to ascertain readiness for spontaneous breathing test and time of extubation.

As much information as possible will be collected about the reasons for missing outcome data; this will be used to inform any imputation approaches employed in the analysis. Such methods will be fully described in the SAP.

IRAS 220853 Page **63** of **87**

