#### 17. Efficacy Evaluations

#### 17.1. Data Sets Analysed

The principle of intention-to-treat, as far as practically possible, will be the main strategy of the analysis adopted for the primary outcome and all secondary outcomes. These analyses will be conducted on all randomised participants, in the group to which they were randomised, and for whom the outcome(s) of interest have been observed/measured. No imputations will be made.

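### The only planned LRSQ comparison adjusts the 12-month score for the 6-month score, itself a post-randomisation outcome, so it does not estimate the total long-term effect; separately, it excludes season 3 and leaves 6 months without a between-arm comparison.

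*SAP*

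**What the plan says.** - **Objective and time points.** Protocol 3.5.3 sets the first secondary objective: "To describe the impact of intervention on infants' long-term respiratory symptoms". Table 1 in Protocol 3.6.2 gives the LRSQ as its only measure, with time points "LRSQ at 6 months and 12 months post randomisation". The schedule in Protocol 8.3 has no LRSQ at baseline.
- **Who completes which form.** Protocol 8.6.1 sends the questionnaire "in all three seasons at 6m, and in addition at 12m to parents of infants recruited in seasons 1 and 2". SAP 17.4.9 agrees: "The parents of infants randomised in season 3 will only complete the 6m questionnaire".
- **The comparison.** SAP 17.4.9.2 fits a linear mixed model by ANCOVA to the "12month LRSQ score with adjustment for 6-month LRSQ score", with the ventilation-time stratum as a fixed effect and site as a random intercept.
- **Missing data.** "This will be a complete case analysis and only fully completed questionnaires will be included in the analysis" (SAP 17.4.9.2), and "No imputations will be made" (SAP 17.1).
- **At 6 months.** The same section gives the number, number missing, mean and SD by arm at 6 months, at 12 months and for the difference where available. It plans no between-arm estimate at 6 months.
- **Protocol method.** Protocol 11.5 says "LRSQ data will be modelled longitudinally and comparisons made between groups".

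**The concern.** ANCOVA on an earlier score is standard when that score is a pre-treatment baseline. Here it is not: the infant was treated about six months before the covariate was measured. If surfactant changes symptoms by 6 months, the adjustment subtracts the share of the 12-month effect that the 6-month score predicts. What remains is a conditional effect. It does not answer the objective, and it loses the full protection of randomisation because treatment may have changed the covariate.

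The SAP uses the sound pattern elsewhere. For the SF ratio (17.4.4.2) it models all post-baseline values and adjusts for the 0-hour value. The LRSQ model borrows the form without having a baseline.

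A second, separate problem is which infants are used. A complete-case model needing both forms cannot include any season-3 infant, nor any season-1 or season-2 infant who lacks either form. The 6-month scores from all three seasons, potentially the larger data set, support no planned comparison. At stake is whether the trial's only long-term respiratory result can be read as an effect of treatment on symptoms.

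**Working it through.** **Figures in the plan.** There is no LRSQ effect size, SD, correlation or power to reproduce. The planned sample does reproduce: 134/0.95 = 141.05, rounded up to 142 per arm and 284 in total (Protocol 11.3).

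**Assumptions (none from the documents).** Equal SDs at both visits, correlation ρ = 0.6, a 12-month effect d12 = 0.4 SD, a third of infants in each season, full response unless stated, two-sided 5%. Per arm, 142 infants then have a 6-month form and 142 × 2/3 ≈ 95 have both.

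**Step 1: what the planned model estimates.** The treatment coefficient is d12 − ρ × (SD12/SD6) × d6, where d6 is the 6-month effect. With equal SDs the share of d12 kept is 1 − ρ × (d6/d12).

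| d6/d12 | ρ = 0.3 | ρ = 0.5 | ρ = 0.6 | ρ = 0.7 |
|---|---|---|---|---|
| 0 | 100% | 100% | 100% | 100% |
| 0.5 | 85% | 75% | 70% | 65% |
| 1 | 70% | 50% | 40% | 30% |
| 1.5 | 55% | 25% | 10% | −5% |

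A simulation with a true effect of −0.40 SD at both visits gave planned-model estimates of −0.28, −0.20 and −0.12 at ρ = 0.3, 0.5 and 0.7. The 12-month difference without the covariate stayed at about −0.40.

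**Step 2: power of the planned model.** Residual SD = √(1 − 0.36) = 0.8, so SE = 0.8 × √(2/95) = 0.116. This ignores the small extra variance that arises when treatment shifts the covariate.
- d6 = d12: 0.4 × 0.40 = 0.16; z = 1.38; power about 28%.
- d6 half of d12: 0.4 × 0.70 = 0.28; z = 2.41; power about 67%.
- d6 = 0: 0.40; z = 3.45; power about 93%.

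**Step 3: power of a repeated-measures model with treatment-by-visit.**
- 12 months: variance per arm = (1 − ρ²)/95 + ρ²/142 = 0.64/95 + 0.36/142 = 0.00927. SE = √(2 × 0.00927) = 0.136; z = 0.4/0.136 = 2.94; power about 84%. This does not depend on d6.
- 6 months, if the effect there is also 0.4 SD: SE = √(2/142) = 0.119; z = 3.37; power about 92%.

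**Step 4: 30% non-response**, taken as random and in the same infants at both visits, so 95 × 0.7 = 66.5 and 142 × 0.7 = 99.4 per arm.
- Repeated measures, 12 months: variance = 0.64/66.5 + 0.36/99.4 = 0.01325; SE = 0.163; z = 2.46; power about 69%.
- Repeated measures, 6 months: SE = √(2/99.4) = 0.142; z = 2.82; power about 81%.
- Planned model: SE = 0.8 × √(2/66.5) = 0.139; z = 1.15, 2.02 and 2.88 for the three cases of Step 2; power about 21%, 52% and 82%.

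**The case against.** The strongest replies, and what stands of each:

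- **The loss is not established.** This stands. The documents give neither ρ nor the 6-month effect. If the effect appears only at 12 months, nothing is lost and the planned model is the more powerful one (about 93% against 84%). A reader might infer that the long-term effect is largely adjusted away. That needs an effect already present at 6 months and a high enough correlation; more than half is lost only if ρ × (SD12/SD6) × (d6/d12) exceeds 0.5.
- **Season 3 has no 12-month data by design.** This also stands: no model can supply those scores. A reader might take the exclusion as a cause of the attenuation. It is not. It costs precision and the 6-month comparison, but does not in expectation shrink the estimate. The share of infants in season 3 is not stated; one third is an assumption.
- **The 6-month scores are reported.** True, as summaries by arm, from which a crude difference could be worked out. What is missing is a planned, adjusted comparison.
- **The objective is to describe, not to test.** Fair as to power, but a description of impact still needs the total effect. SAP 11 also aims to test superiority in all outcomes, and the SAP does fit a model here.
- **The protocol names no particular longitudinal model.** Correct. The supplied protocol's amendment log ends at version 2.0, while the SAP cites versions 3.0 and 6.0. A reader might infer a breach of the governing protocol, but that text was not available. The defect lies in the SAP's own wording and does not depend on it.

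**Conclusion.** The point holds in limited form. The planned estimate is the part of the 12-month effect not carried by the 6-month score, so it does not estimate the total effect at either visit. That follows from the model alone. Season-3 infants are excluded and no between-arm comparison is planned at 6 months; these follow from the SAP's text and are a separate weakness.

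The size is conditional. At ρ = 0.6 the share kept runs from 40% (constant effect) to 100% (no 6-month effect), with power from about 28% to 93% under the stated assumptions. If the 6-month effect were 1.5 times the 12-month one and ρ were 0.7, the estimate would take the opposite sign.

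One comparison should be avoided. A single effect pooled over both visits has information 95 × 2/1.6 + 47 = 165.75 per arm, SE = √(2/165.75) = 0.110, z = 3.64 and power about 95%. Setting that against 28% compares different questions; the per-visit figures of 84% and 92% are the relevant ones.

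This is one secondary outcome. The primary analysis, the safety analyses and data collection are unaffected. It should be corrected, but it ranks below a mandatory change.

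**What to change.** In SAP 17.4.9.2, remove the 6-month score as a covariate. Fit a linear mixed model with the 6- and 12-month scores both as outcomes and with terms for treatment, visit, treatment-by-visit and the ventilation-time stratum, a random intercept for site, and a within-infant correlation. Include every infant with at least one fully completed questionnaire. Report the between-arm difference with its 95% CI at 6 months (all seasons) and at 12 months (forms from seasons 1 and 2). Keep the descriptive table.

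The cost is a paragraph of SAP text and a different model call, with no new data. It also sits comfortably with the longitudinal modelling in Protocol 11.5. The change should be dated before the randomisation codes are released to the statistical team; if that has passed, label it as a later addition.

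There are two downsides. If the effect appears only at 12 months, power there is lower than in the planned model (about 84% against 93% under the assumptions above). The 12-month estimate also borrows from season-3 6-month scores, which assumes the relation between visits is similar across seasons; a 12-month comparison restricted to seasons 1 and 2 without the 6-month score (about 79% power: 0.4/√(2/95) = 2.76) would serve as a check.

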14.2 Data Capture Methods

The study case report form (CRF) is the primary data collection instrument for the study. All data requested on the CRF must be recorded. All missing data must be explained.

Please ensure documents are sent by sites separate to the consent form as this has patient identifiable data on it.

The LRSQ will be completed by participants' parents at 6m and 12m after randomisation. These are completed online but paper copies will be available on request for parents without internet access. If paper questionnaires are used **sites should photocopy them** in order to retain a copy at site before mailing originals to CTRC.

BESS will also be collecting data from the Paediatric Intensive Care Audit Network (PICANet). PICANet is a secure confidential high-quality clinical database, recording details of the treatment of all critically ill children in PICUs. Collection of personally identifiable data

IRAS 220853 Page **73** of **87**

has been approved by the Patient Information Advisory Group (now the NHS Health Research Authority Confidentiality Advisory Group) and ethical approval granted by the Trent Medical Research Ethics Committee.

PICANet will provide a bespoke download page for the trial and sites will regularly download their own data for consented BESS patients only and transfer this to the CTRC.

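### The LRSQ analysis discards a whole form for one blank item out of 32 and needs two complete forms per infant; the loss of precision is avoidable, but its size depends on an item non-response rate the documents do not give.

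*SAP*

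**What the plan says.** SAP 17.4.9.1 describes the instrument: "The LRSQ consists of eight domains, each containing between three and five items". Each item is scored 0 to 4. The SAP plans a score for each domain as well as a total with a maximum of 128.

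SAP 17.4.9.2 sets the inclusion rule: the analysis is complete-case, and "only fully completed questionnaires will be included in the analysis". The one comparative model is for the 12-month "LRSQ score with adjustment for 6-month LRSQ score and the stratification factors of time on" ventilation before randomisation, with site as a random intercept. SAP 17.4.9 adds: "The parents of infants randomised in season 3 will only complete the 6m questionnaire".

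SAP 17.1 says of the efficacy analyses in general: "No imputations will be made". SAP 18 requires missing data to be quantified, with reasons where known. Sensitivity analyses are given for the primary outcome (SAP 17.4.1.2 and 19) and for readiness for a breathing test (SAP 17.4.2.2), but none for the LRSQ.

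On mode of completion, Protocol 14.2 says: "These are completed online but paper copies will be available on request for parents without internet access". Protocol 8.6.1 also describes a web form with a paper version. Neither document says whether online items are mandatory.

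**The concern.** A complete-case rule set at the level of the whole form is strict for a 32-item instrument. A parent who answers 31 items contributes nothing, not even the seven or more domains with no blank. The comparative model applies the rule twice, because an infant enters only if the 6-month and 12-month forms are both complete.

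The LRSQ carries Secondary Objective 1 (Protocol 3.5.3) and is the only trial outcome measured at 6 and 12 months; mortality and readmission stop at 90 days. Its sample is already cut by unreturned forms and by the absence of a 12-month form in season 3. What is at stake is further loss of precision that a scoring rule could largely avoid.

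**Working it through.** **Item count, checked against the plan's own maximum.** The domain table in SAP 17.4.9.1 gives 4 + 4 + 4 + 4 + 5 + 3 + 4 + 4 = 32 items. At 4 points each, 32 × 4 = 128, which is the stated maximum. The item count is secure.

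**Loss under the SAP rule, independent skipping.** Let q be the probability that an item is left blank. The documents give no value, so q is assumed. A form is lost with probability 1 − (1 − q)^32. A 6- and 12-month pair, both returned, is lost with probability 1 − (1 − q)^64. Relative to using all returned pairs, the standard error grows by 1/√[(1 − q)^64].

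| q (assumed) | Single form lost | Pair lost | Standard error multiplier |
|---|---|---|---|
| 0.1% | 3.2% | 6.2% | 1.03 |
| 0.5% | 14.8% | 27.4% | 1.17 |
| 1% | 27.5% | 47.4% | 1.38 |
| 2% | 47.6% | 72.6% | 1.91 |

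For comparison, a four-item domain scored on its own is lost with probability 1 − (1 − q)^4, which is 2.0, 3.9 or 7.8% at q = 0.5, 1 or 2%.

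**Clustered skipping.** If the blanks come from the same few parents, fewer forms are affected. A beta-binomial model with the same mean and an assumed intraclass correlation of 0.05 to 0.3 gives a single-form loss of 3.3-9.1% at q = 0.5%, 6.6-17.4% at 1% and 12.7-31.9% at 2%. Whatever the dependence between a parent's two forms, if each form is lost with probability f, the pair loss lies between f and 2f. At q = 1% that is somewhere between 6.6% and 2 × 17.4 = 34.8%.

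**Mandatory online items.** If the web form forces an answer to each item, submitted online forms lose nothing to this rule and only paper forms are exposed.

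**In infants.** Assume equal recruitment over three seasons and that a share r of families in seasons 1 and 2 return both forms. The number of returned pairs is 284 × 2/3 × r: 95, 133 or 170 for r = 50, 70 or 90%. With independent skipping at 1% (multiply by 0.99^64 = 0.526), 50, 70 or 90 remain.

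**Bias.** The SAP's adjustment for the 6-month score was simulated with 400,000 infants per arm. Assumed inputs were a mean score of 25, SD 15, a slope of 0.5 of the 12-month on the 6-month score, residual SD 13, and 1% item non-response at the mean score. About half of the pairs were lost.

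| Skipping pattern | True difference | Estimate from complete pairs |
|---|---|---|
| Unrelated to score | −5 | −5.02 |
| Higher scorers skip more, same in both arms | 0 | 0.02 |
| Higher scorers skip more, same in both arms | −5 | −4.73 |
| Score-related skipping in one arm only | 0 | −1.76 |

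A false difference under no effect arose only when the link between score and skipping differed by arm.

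**Effect of a domain-level rule.** Suppose a domain is prorated when at least half its items are answered, and a form is lost only if some domain falls short. With independent skipping, 0.03% of forms are lost at q = 1% and 0.15% at q = 2%, against 27.5% and 47.6% under the SAP rule.

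**The case against.** The strongest reply is that the size of the loss is not in the documents. Any item non-response rate is an assumption, and independent skipping is the least favourable pattern for whole-form loss. Paper is the fallback, offered on request, and its existence says nothing about blanks on the web form. Protocol 14.3.2 provides for checking received data for missing values and querying them, though it does not say whether this reaches parent questionnaires. All of this stands, so the loss must be given as a range that starts at zero for online forms.

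A reader might infer that the rule biases the treatment comparison because parents who skip items may differ in symptom burden. The documents do not support that. Such a difference, if equal in both arms, creates no false effect. A mechanism that differs by arm is not described, and parents are meant to remain blinded (Protocol 9.4.3).

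Two further objections stand. Scoring complete domains does not restore a missing total, and the SAP specifies no treatment comparison by domain, so the gain there is descriptive. Prorating is a form of imputation and conflicts with SAP 17.1, and the instrument's own scoring rule cannot be checked from the documents.

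Finally, the loss would be visible. The LRSQ summaries include the number missing, and SAP 18 reports missingness for all outcomes. Visibility does not recover the data.

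**Conclusion.** The concern holds as a matter of avoidable lost precision. It is certain that one blank among 32 items excludes the form, that fully answered domains go with it on a literal reading, that the model needs two complete forms, and that neither an imputation rule nor an LRSQ sensitivity analysis softens this.

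The size is conditional. At an assumed 0.5, 1 or 2% of items blank, single-form loss is 15, 28 or 48% under independence and about 3-9, 7-17 or 13-32% with clustering. Pair loss under independence is 27, 47 or 73%. With mandatory online items, only paper forms are exposed. A reader might take the 28% or 47% as a forecast; they are illustrations at one assumed rate and one pattern of skipping. Between-arm bias remains possible but is not shown.

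This is a secondary outcome, and neither the primary analysis nor the sample size is touched. The absence of season 3 from the 12-month model is a separate and certain loss that a form-completion rule does not repair.

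**What to change.** Change SAP 17.4.9 before the randomisation codes are released to the statistical team:

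1. State whether online items are mandatory.
2. Report each domain score whenever all items of that domain are answered, regardless of blanks elsewhere on the form.
3. Prespecify a part-completed-form rule for the total score. Use the instrument's published rule if there is one. Otherwise prorate a domain when at least half its items are answered (mean of the answered items × number of items in the domain), and sum the eight domain scores.
4. Record this as an explicit exception to the bar on imputation in SAP 17.1.
5. Report the fully-completed-form analysis alongside it as a sensitivity analysis.

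The cost is SAP wording and a little programming, with no new data collection. The downside is a mild assumption that the few unanswered items in a domain resemble the answered ones; the sensitivity analysis shows how far the result depends on it.
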